**SAMPLE SIZE DETERMINATION:**

Patients will be enrolled until there are 120 patients in the CRABC m-MITT Population in Part A. The study will have 80% power to demonstrate non-inferiority between Group 1 and Group 2 using a 20% non-inferiority margin and a 2-sided 95% CI. This assumes a mortality rate in the comparator group (Group 2) of 41% and in the ETX2514SUL group (Group 1) of 36%. To have 120 patients in the CRABC m-MITT Population, Part A will need to enroll approximately 200 patients, assuming 60% of ABC clinical isolates are carbapenem-resistant. Patient enrollment in Part B (Group 3) will continue until Part A enrollment in the CRABC m-MITT Population is complete. Rates of carbapenem resistance among isolates from Part A patients will be monitored by the unblinded data manager/designee at the Clinical Research Organization on an ongoing basis.

---

**SITES:** Approximately 100 global sites.

---

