### 9.2.2 Analysis of Efficacy

#### 9.2.2.1 Primary efficacy analysis

The primary efficacy endpoint for the study is 28-day all-cause mortality in the CRABC m-MITT Population in Part A. Patients in the CRABC m-MITT Population who discontinue study drug prematurely in Part A for any reason will be included in the assessment of 28-day all-cause mortality, provided consent has not been withdrawn.

A sensitivity analysis for the primary efficacy endpoint will be performed for patients whose eligible culture is >48 hours from the first dose of study drug, as well as for all patients with and without evidence of non-susceptibility to colistin and ETX2514SUL at baseline. Details of the sensitivity analysis will be described in the SAP.

The non-inferiority assessment will be based on the 2-sided 95% confidence intervals (CIs) for the difference ( $[\text{ETX2514SUL} + \text{imipenem/cilastatin}] - [\text{colistin} + \text{imipenem/cilastatin}]$ ) in 28-day all-cause mortality rates between the treatment groups. Non-inferiority will be concluded if the upper limit of the 2-sided 95% CI is less than +20%.

If non-inferiority is achieved, a test of superiority will be performed.

The analysis of the primary efficacy endpoint 28-day all-cause mortality will also be performed in the ITT Population.

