#### 9.2.5 Sample Size Determination

Patients will be enrolled until there are 120 patients in the CRABC m-MITT Population in Part A. The study will have 80% power to demonstrate non-inferiority between Group 1 and Group 2 using a 20% non-inferiority margin and a 2-sided 95% CI. This assumes a mortality rate in the comparator group (Group 2) of 41% and in the ETX2514SUL group (Group 1) of 36%. To have 120 patients in the CRABC m-MITT Population, Part A will need to enroll approximately 200 patients, assuming 60% of ABC clinical isolates are carbapenem-resistant. Patient enrollment in Part B (Group 3) will continue until Part A enrollment in the CRABC m-MITT Population is complete. Rates of carbapenem resistance among isolates from Part A patients will be monitored by the unblinded data manager/designee at the Clinical Research Organization on an ongoing basis.

[Table 7](#) demonstrates the mortality rates in the ETX2514SUL plus imipenem/cilastatin treatment group required to demonstrate non-inferiority or superiority with no less than 80% power in the CRABC m-MITT Population relative to various 28-day all-cause mortality rates in the colistin plus imipenem/cilastatin treatment group, given 120 patients in the CRABC m-MITT Population.

The sample size of 120 patients in the CRABC m-MITT Population was calculated based on a 41% mortality rate in the colistin plus imipenem/cilastatin treatment group.

**Table 7. 28-Day All-Cause Mortality Rates in the CRABC m-MITT Population Required to Demonstrate Non-Inferiority and Superiority**

ETX2514SUL+IMI	Colistin+IMI	95% CI for Treatment Difference [1]	Power	Test
39%	45%	(-0.24, 0.12)	82%	Demonstrate NI
21%	45%	(-0.40, -0.08)	80%	Demonstrate superiority
35%	40%	(-0.22, 0.12)	80%	Demonstrate NI
17%	40%	(-0.39, -0.07)	80%	Demonstrate superiority
30%	35%	(-0.22, 0.12)	83%	Demonstrate NI
13%	35%	(-0.37, -0.07)	81%	Demonstrate superiority
26%	30%	(-0.20, 0.12)	83%	Demonstrate NI
9%	30%	(-0.35, -0.07)	83%	Demonstrate superiority

1. 95% CIs for treatment difference ([ETX2514SUL + IMI] – [colistin + IMI]) were calculated using a normal approximation to the binomial distribution.  
CI = confidence interval; CRABC = Carbapenem-resistant *Acinetobacter baumannii-calcoaceticus* complex; ETX2514SUL = sulbactam-ETX2514; IMI = imipenem/cilastatin; m-MITT = Microbiologically Modified Intent-to-Treat; NI = non-inferiority.

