## **3. STUDY DESIGN**

### **3.1. General Study Design**

This study is a randomized, active-controlled study to evaluate the safety and efficacy of IV ETX2514SUL in patients with ABC infections. Patients providing informed consent and meeting all study eligibility criteria will be enrolled in the study and have pretreatment blood and infection site-specific samples obtained and submitted to the local laboratory.

The study will be enrolled in 2 parallel parts, with the PK data from the first approximately 30 patients in Part A (with only 15 patients dosed with ETX2514SUL) reviewed prior to initiating enrollment in Part B:

- a. Part A will be the pivotal, assessor-blind, randomized, comparative portion of the study in patients with documented ABC HABP, VABP, VP, or bacteremia. While study drugs will not be masked due to logistical reasons, every attempt will be made to maintain the blind for patients, all staff at the site, and the Sponsor or its designees, except for the treatment physician and other immediate healthcare providers. In Part A, patients will be randomized 1:1 to 1 of the following treatment groups:
  - Group 1: 1.0 g ETX2514/1.0 g sulbactam IV infused over 3 hours every 6 hours (q6h) plus 1.0 g imipenem/1.0 g cilastatin IV infused over 1 hour q6h; or
  - Group 2: 2.5 mg/kg colistin IV infused over 30 minutes every 12 hours (q12h) plus 1.0 g imipenem/1.0 g cilastatin IV infused over 1 hour q6h.

Patients will be enrolled until there are at least 120 patients in the CRABC Microbiologically Modified Intent-to-Treat (m-MITT) Population in Part A, as determined by the central microbiology laboratory. Approximately 200 patients are expected to be enrolled in Part A, assuming approximately 60% of patients will have CRABC (see the statistical methods for complete details). The HABP/VABP/VP patients who are randomized to Part A based on a positive screening of a respiratory sample for ABC by the Biofire FilmArray Pneumonia Panel (BPP), but who subsequently do not have growth of ABC in their respiratory sample culture processed by the local microbiology laboratory, will be withdrawn from the study drug treatment.

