#### **4. SAMPLE SIZE JUSTIFICATION**

Patients will be enrolled until there are 120 patients in the CRABC m-MITT Population in Part A. The study will have 80% power to demonstrate non-inferiority between Group 1 and Group 2 using a 20% non-inferiority margin and a 2-sided 95% CI. This assumes a mortality rate in the comparator group (Group 2) of 41% and in the ETX2514SUL group (Group 1) of 36%. To have 120 patients in the CRABC m-MITT Population, Part A will need to enroll approximately 200 patients, assuming 60% of ABC clinical isolates are carbapenem-resistant. Patient enrollment in Part B (Group 3) will continue until Part A enrollment in the CRABC m-MITT Population is complete. Rates of carbapenem resistance among isolates from Part A patients will be monitored by the unblinded data manager/designee at the Clinical Research Organization on an ongoing basis.

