#### **9.3.1. Primary Efficacy Analyses**

The primary efficacy endpoint for the study is 28-day all-cause mortality in the CRABC m-MITT Population in Part A. Patients in the CRABC m-MITT Population who discontinue study drug prematurely in Part A for any reason will be included in the assessment of 28-day mortality, provided consent has not been withdrawn. Patients who withdraw consent from the survival status will be excluded from the analysis. Patients who have missing survival status will be treated as death. Patients who were randomized into Part A but then transferred into Part B will not be included in Part A analysis.

The non-inferiority assessment will be based on the 2-sided 95% confidence intervals (CIs) computed using a continuity-corrected Z-statistic for the difference ( $[\text{ETX2514SUL} + \text{imipenem/cilastatin}] - [\text{colistin} + \text{imipenem/cilastatin}]$ ) in 28-day all-cause mortality rates between the treatment groups. Non-inferiority will be concluded if the upper limit of the 2-sided 95% CI is less than +20%. If non-inferiority is achieved, the superiority will be investigated. Superiority will be concluded if the upper limit of the 2-sided 95% CI is less than 0.

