### 9.3.2. Secondary Efficacy Analyses

The secondary efficacy endpoints for Part A and Part B include the following:

- 28-day all-cause mortality in the ITT Population;
- Clinical cure at TOC in the CRABC m-MITT Population;
- Clinical cure at TOC in the m-MITT, Clinical Evaluable (CE), Microbiologic Evaluable (ME), and CRABC ME Populations;
- Clinical cure at EOT, and LFU in the m-MITT, CRABC m-MITT, CE, ME, and CRABC ME Populations;
- Microbiological favorable assessment at EOT, TOC, and LFU by overall, monomicrobial infection and polymicrobial infection in the m-MITT, CRABC m-MITT, ME, and CRABC ME Populations. Monomicrobial infection is defined as subjects with only ABC pathogens isolated at Baseline, Polymicrobial infection is defined as subjects with both ABC pathogens and non-ABC pathogens isolated at Baseline;
- 14-day all-cause mortality in the CRABC m-MITT and m-MITT Populations; and
- 28-day all-cause mortality in the m-MITT and CRABC ME Populations.

All secondary efficacy analyses will be analyzed including the patients who withdraw consent from the survival status.

In addition, the primary analysis will be repeated for 28-day all-cause mortality in the ITT, m-MITT and CRABC ME Populations excluding the patients who withdraw consent from the survival status for Part A. 14-day all-cause mortality in the CRABC m-MITT and m-MITT Populations will be performed in a same manner excluding the patients who withdraw consent prior to Day 14 for Part A.

Similarly, the analysis of clinical response and the microbiologic response will be repeated excluding patients who withdraw consent from the survival status in the CRABC m-MITT Population for Part A.

The number and percentage of patients in each response category for the secondary efficacy endpoints will be summarized by treatment group. Two-sided 95% CIs computed using a continuity-corrected Z-statistic for the difference in outcome rates between the treatment groups in Part A will be provided. Patients who initially randomized to Part A and transferred to Part B will not be included in Part A analysis and will be included in Part B analysis from the time point of transfer. Patients with a missing secondary efficacy value, the efficacy variable will be considered as non-responder. In addition, time to death will be analyzed using log rank test between the treatment groups for Part A.

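### The stated 80% power belongs to an uncorrected interval; the SAP's continuity-corrected interval gives about 75% at 120 patients

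*SAP*

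**What the plan says.** - **Planned power.** Protocol 9.2.5 states: "The study will have 80% power to demonstrate non-inferiority between Group 1 and Group 2 using a 20% non-inferiority margin". The inputs are 120 patients in the CRABC m-MITT Population, 28-day mortality of 41% on colistin and 36% on ETX2514SUL, and a two-sided 95% interval. The synopsis gives the same statement, and SAP 4 repeats it: "The study will have 80% power to demonstrate non-inferiority".
- **Sizing table.** The footnote to Protocol Table 7 says its intervals "were calculated using a normal approximation to the binomial distribution". It mentions no continuity correction.
- **Primary analysis in the protocol.** Protocol 9.2.2.1 says: "The non-inferiority assessment will be based on the 2-sided 95% confidence intervals (CIs) for the difference". It is silent on how the interval is computed.
- **Primary analysis in the SAP.** SAP 9.3.1 specifies "2-sided 95% confidence intervals (CIs) computed using a continuity-corrected Z-statistic for the difference". Non-inferiority requires an upper limit below +20%. No formula for the correction is given.
- **Secondary analyses.** SAP 9.3.2 uses the same method: "Two-sided 95% CIs computed using a continuity-corrected Z-statistic for the difference in outcome rates".
- **Enrolment.** SAP 3.1 says: "Patients will be enrolled until there are at least 120 patients in the CRABC" m-MITT Population. SAP 4 and the protocol plan on 120.

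**The concern.** A continuity correction widens the interval, so at a fixed sample size it lowers the chance that the upper limit falls below the margin. If the 80% was computed without the correction, the pre-specified primary analysis of the pivotal Part A has less power than the documents state.

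The missing formula matters too, because the method can decide a close result. Take 60 per arm with 25 deaths on ETX2514SUL and 24 on colistin. The uncorrected upper limit is just under 20% and passes; with the usual correction it is just over 20% and fails.

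**Working it through.** **Inputs from the documents:** pT = 0.36, pC = 0.41, margin 0.20, two-sided 95% (z = 1.96), N = 120, 1:1 randomisation.

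**Assumptions:** 60 analysed per arm; correction c = 0.5(1/n1 + 1/n2), which at 60/60 is 1/60 = 0.0167. A half-size correction, c = 0.0083, is shown for range.

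**1. Reproduce the stated 80%.**

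SE = sqrt(0.36×0.64/60 + 0.41×0.59/60) = 0.0887

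Power = Φ[(0.20 + 0.05)/0.0887 − 1.96] = 80.5%

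Exact binomial enumeration of the same uncorrected interval gives 80.6%.

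**2. Apply the correction.** Power = Φ[(0.25 − c)/0.0887 − 1.96].

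| Interval, 60/60 | Normal approximation | Exact |
|---|---|---|
| Uncorrected | 80.5% | 80.6% |
| Usual correction | 74.9% | 74.8% |
| Half correction | 77.8% | 78.1% |

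With the usual correction, exact power for splits (ETX2514SUL/colistin) from 57/63 to 63/57 runs from 73.1% to 77.2%.

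**3. Check against Table 7, non-inferiority rows (60 per arm).**

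| Rates | Stated power | Uncorrected | Usual correction | Half correction | Stated upper limit | Uncorrected limit | Corrected limit (usual) |
|---|---|---|---|---|---|---|---|
| 39% vs 45% | 82% | 82.4% | 77.2% | 79.9% | 0.12 | 0.116 | 0.133 |
| 35% vs 40% | 80% | 80.8% | 75.3% | 78.2% | 0.12 | 0.123 | 0.140 |
| 30% vs 35% | 83% | 83.3% | 78.0% | 80.8% | 0.12 | 0.117 | 0.134 |
| 26% vs 30% | 83% | 83.4% | 77.8% | 80.8% | 0.12 | 0.121 | 0.137 |

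The printed powers and limits all fit the uncorrected interval. None of the four rows fits the corrected one.

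**4. Sample size for 80% with the usual correction.** At 128 patients power is 77.9% (exact 78.1%). Exact power reaches 80.3% at 132. The normal approximation gives 79.95% at 134 and 80.6% at 136. So 132 (exact) to 136 (normal approximation) patients are needed.

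**5. The borderline example.** 25/60 versus 24/60: difference 0.0167, SE 0.0897, 1.96×SE = 0.1759. The upper limit is 0.1925 uncorrected and 0.1925 + 0.0167 = 0.2092 corrected.

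**6. Type I error.** At 61% versus 41%, 60 per arm, the exact one-sided error is 2.6% uncorrected and 1.7% with the usual correction, against a nominal 2.5%.

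**The case against.** - **The 80% is not miscalculated.** It is right for an uncorrected interval. Protocol 9.2.2.1 does not exclude a correction, and Protocol 9.2 leaves the detail to the SAP. This stands: the fault is a mismatch between the sizing and the analysis. That the 80% is uncorrected is inferred from reproducing it, since no document says so, and the Table 7 footnote describes the intervals, not the powers. The agreement in all four non-inferiority rows makes the inference strong.
- **The 75% rests on an assumed formula and split.** This also stands. With half the correction, power at the planning rates is about 78%, and two Table 7 rows stay near 81%. The direction is not in doubt, because a correction can only widen the interval. The calculation also leaves out the SAP 9.3.1 rules that count missing survival status as death and exclude patients who withdraw consent.
- **SAP 3.1 treats 120 as a floor.** An overshoot would recover some power, but 128 patients still give only about 78%, and SAP 4 plans on 120.
- **The planning rates matter more.** With equal mortality of 41% in both arms, exact power is 61% uncorrected and 54% corrected. Losing the assumed 5-point advantage costs about 20 points; the correction costs about 6. This puts the size in proportion but does not make the stated 80% right.
- **The correction is conservative and harms no patient.** Agreed. It affects the stated power, not the validity of a positive result.

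**Conclusion.** The concern holds. The interval that SAP 9.3.1 prescribes does not deliver the 80% power that SAP 4 and the protocol state. At the planning rates with 120 patients, power is about 75% under the usual correction and a 60/60 split, and about 73% to 78% over the splits and correction sizes examined. That it is below 80% is firm; the exact figure is less so, because the SAP states neither the correction nor the split. Under the usual correction the chance of missing non-inferiority rises from about 20% to about 25%. This should be fixed, but a positive result would remain valid.

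**What to change.** **Default.**
- In SAP 9.3.1, write out the interval, for example d ± [1.96·sqrt(p1q1/n1 + p2q2/n2) + 0.5(1/n1 + 1/n2)].
- Restate the power as about 75% in SAP 4, Protocol 9.2.5 and the synopsis.
- Recompute Table 7 for the same interval, including the superiority rows. Under the usual correction these fall to about 77%, 76%, 77% and 79%, against 80%, 80%, 81% and 83% stated. The sentence introducing the table promises at least 80% power, so either it or the tabulated rates must change.

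The cost is wording and one table, with no change to conduct, analysis or patient numbers, and a lower disclosed power. SAP 4 can be corrected at once. The protocol text needs an amendment under Protocol 12.1 and can wait for the next one.

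**Alternative, only before unblinding.** Use the uncorrected interval behind the sample size, or a score interval (Miettinen-Nurminen), in both SAP 9.3.1 and SAP 9.3.2. Either gives 80.6% exact power at 60/60. The cost is that exact one-sided error at 61% versus 41% rises from about 1.7% to about 2.6%. It also gives up a conservative pre-specified rule in a trial whose site staff are unblinded, so a late change made to gain power would be hard to defend.

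**To keep both the correction and 80% power,** the target would have to be about 132 to 136 CRABC m-MITT patients. At the plan's 60% carbapenem-resistance rate that is about 220 to 227 enrolled (132/0.6 to 136/0.6) instead of 200.

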#### **Sensitivity Analyses**

Sensitivity analyses of the primary efficacy endpoint will be conducted as follows:

- Analysis of the primary efficacy endpoint will be performed for patients whose eligible culture is >48 hours prior to the first dose of treatment in the CRABC m-MITT Population.
- Analysis of the primary efficacy endpoint will be performed for patients whose eligible culture is ≤48 hours prior to the first dose of treatment in the CRABC m-MITT Population.
- Analysis of the primary efficacy endpoint will be performed for patients with ABC pathogens susceptible to ETX2514SUL and colistin at baseline in the CRABC m-MITT Population.
- Analysis of the primary efficacy endpoint will be performed for patients without ABC susceptibility results for ETX2514SUL or colistin at baseline in the CRABC m-MITT Population.
- Analysis of the primary efficacy endpoint will be performed including the patients who were randomized into Part A but then transferred into Part B in the ITT Population.
- Analysis of the primary efficacy endpoint will be performed excluding the patients who have missing survival status in the CRABC m-MITT Population.

Analysis of the primary efficacy endpoint and the sensitivity analysis will be repeated including the patients who withdraw consent from the survival status.

### 9.3.2. Secondary Efficacy Analyses

The secondary efficacy endpoints for Part A and Part B include the following:

- 28-day all-cause mortality in the ITT Population;
- Clinical cure at TOC in the CRABC m-MITT Population;
- Clinical cure at TOC in the m-MITT, Clinical Evaluable (CE), Microbiologic Evaluable (ME), and CRABC ME Populations;
- Clinical cure at EOT, and LFU in the m-MITT, CRABC m-MITT, CE, ME, and CRABC ME Populations;
- Microbiological favorable assessment at EOT, TOC, and LFU by overall, monomicrobial infection and polymicrobial infection in the m-MITT, CRABC m-MITT, ME, and CRABC ME Populations. Monomicrobial infection is defined as subjects with only ABC pathogens isolated at Baseline, Polymicrobial infection is defined as subjects with both ABC pathogens and non-ABC pathogens isolated at Baseline;
- 14-day all-cause mortality in the CRABC m-MITT and m-MITT Populations; and
- 28-day all-cause mortality in the m-MITT and CRABC ME Populations.

All secondary efficacy analyses will be analyzed including the patients who withdraw consent from the survival status.

In addition, the primary analysis will be repeated for 28-day all-cause mortality in the ITT, m-MITT and CRABC ME Populations excluding the patients who withdraw consent from the survival status for Part A. 14-day all-cause mortality in the CRABC m-MITT and m-MITT Populations will be performed in a same manner excluding the patients who withdraw consent prior to Day 14 for Part A.

Similarly, the analysis of clinical response and the microbiologic response will be repeated excluding patients who withdraw consent from the survival status in the CRABC m-MITT Population for Part A.

The number and percentage of patients in each response category for the secondary efficacy endpoints will be summarized by treatment group. Two-sided 95% CIs computed using a continuity-corrected Z-statistic for the difference in outcome rates between the treatment groups in Part A will be provided. Patients who initially randomized to Part A and transferred to Part B will not be included in Part A analysis and will be included in Part B analysis from the time point of transfer. Patients with a missing secondary efficacy value, the efficacy variable will be considered as non-responder. In addition, time to death will be analyzed using log rank test between the treatment groups for Part A.

In Part A, if there is a discrepancy between the assessment of the blinded assessor and unblinded Investigator for clinical outcome, the assessment from the blinded assessor will be used. If there is a missing assessment from either the blinded assessor or unblinded Investigator, the other available assessment will be used.

Part B data will be summarized separately from Part A using descriptive statistics. Patients who transfer from Part A to Part B, Part B data will be summarized from the time point of transfer.

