### 2.2. Secondary Objectives

The secondary objectives of this study are the following:

- To compare the efficacy of ETX2514SUL plus imipenem/cilastatin to colistin plus imipenem/cilastatin in all randomized patients in Part A;
- To evaluate the efficacy of ETX2514SUL plus imipenem/cilastatin in patients with colistin- or polymyxin B-resistant ABC infections in Part B;
- To estimate the efficacy of ETX2514SUL plus imipenem/cilastatin for each primary infection site;
- To evaluate and compare the safety of ETX2514SUL and colistin;
- To describe the overall safety profile of ETX2514SUL; and
- To determine the systemic exposure of ETX2514 and sulbactam in a small cohort of severely ill patients administered ETX2514SUL in Part A.

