### **8.1. Intent-to-Treat Population (ITT)**

The ITT Population will include all patients randomized to study drug treatment (ETX2514SUL plus imipenem/cilastatin or colistin plus imipenem/cilastatin) in Part A or enrolled in Part B, regardless of whether the patient actually receives study drug.

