#### **9.1.3. Baseline Definition**

For microbiological data, baseline pathogen(s) are determined from the specimens collected prior to the first dose of study drug.

For all efficacy and safety endpoints, baseline is defined as the last measurement or assessment prior to the first dose of study drug.

For safety endpoints, patients who were randomized into Part A then transferred into Part B will be included in both Part A and Part B, baseline is defined as the last measurement or assessment prior to the first dose of study drug of Part A for both Part A and Part B safety analysis.

For efficacy endpoints, patients who were randomized into Part A then transferred into Part B will be included in Part B only, baseline is defined as the last measurement or assessment prior to the first dose of study drug of Part A for Part B efficacy analysis.

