### **9.3. Efficacy Analyses**

The efficacy analyses will be analyzed for Part A and Part B separately. Patients who were randomized into Part A and stayed in Part A will be summarized/analyzed only for Part A. Patients who were randomized into Part A but then transferred into Part B will be summarized/analyzed only for Part B.

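### The SAP's secondary ITT analysis of 28-day mortality omits patients transferred from Part A to Part B, so it is not intent-to-treat; the version that includes them is only a sensitivity analysis

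*SAP*

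**What the plan says.** **Population and objective.** SAP 8.1: "The ITT Population will include all patients randomized to study drug treatment", in Part A or enrolled in Part B, whether or not dosed, with no exception for transfer. The first secondary objective in SAP 2.2 is "To compare the efficacy of ETX2514SUL plus imipenem/cilastatin to colistin plus imipenem/cilastatin in all randomized patients in Part A". The first secondary endpoint in SAP 5.2 and 9.3.2 is 28-day all-cause mortality in ITT.

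**Transfer rule.** SAP 9.3: "Patients who were randomized into Part A but then transferred into Part B will be summarized/analyzed only for Part B". SAP 9.1.3, on efficacy endpoints: "patients who were randomized into Part A then transferred into Part B will be included in Part B only". SAP 9.3.2 repeats the rule for the secondary endpoints: "Patients who initially randomized to Part A and transferred to Part B will not be included in Part A analysis".

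**Protocol.** Protocol 9.1 lists transfer as a ground for exclusion from the CRABC m-MITT Population only; its ITT definition has no such exclusion. Protocol 9.2.2.1: "The analysis of the primary efficacy endpoint 28-day all-cause mortality will also be performed in the ITT Population", again with no carve-out.

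**Sensitivity analysis.** SAP 9.3.1 lists an analysis of the primary endpoint "including the patients who were randomized into Part A but then transferred into Part B in the ITT Population". It does not say in which arm the transferred patients are counted.

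**The concern.** The primary population is already selected by laboratory results that arrive after randomization. The ITT mortality result is the natural check on that selection, and it can do the job only if it keeps everyone randomized.

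Transfer follows the local laboratory's finding that the baseline isolate is resistant to colistin or polymyxin B (Protocol 3.1 and 7.7). A patient with such an isolate who dies before the result stays in Part A and counts as a death. One who lives long enough to transfer leaves both numerator and denominator. The exclusion thus depends on survival, and survival to transfer could differ by arm. Treating staff are unblinded (Protocol 5.4). Protocol 3.1 and 7.7 also differ on what happens to such a patient while Part B is not open, and those passages need reconciling, because they affect who stays in Part A.

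At stake is a secondary endpoint labelled ITT that departs from its own definition, alongside a second ITT mortality result built on a different set of patients.

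**Working it through.** **1. Design figures.** With 41% v 36% mortality, a 20-point margin and 60 per arm, SE = sqrt[(0.41 x 0.59 + 0.36 x 0.64)/60] = 0.0887. Power = Phi[(0.20 + 0.05)/0.0887 - 1.96] = 80.5%, which matches the stated 80% with 120 patients. Enrolment: 120/0.60 = 200, as stated. Neither figure depends on how ITT handles transfers.

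**2. The texts side by side.**

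| Place | Are transferred patients in the Part A comparison? |
|---|---|
| SAP 8.1, ITT definition | Yes |
| SAP 2.2, all-randomized objective | Yes |
| Protocol 9.1 and 9.2.2.1, ITT | Yes (no exclusion stated) |
| SAP 9.1.3, 9.3, 9.3.2 | No |
| SAP 9.3.1, sensitivity bullet | Yes, arm not stated |
| CRABC m-MITT, both documents | No, by definition |

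The first three rows and the fourth cannot all be followed for the ITT endpoint. The repeat of that endpoint in SAP 9.3.2 that leaves out consent withdrawals has the same gap: it reuses the primary analysis, which also omits transfers.

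**3. Illustrative size.** The documents give no number or rate of transfers, so these are assumptions:
- 100 randomized per arm (from about 200, 1:1);
- mortality p = 41% (colistin) and 36% (ETX2514SUL) in patients without a locally resistant isolate, borrowed from the sample size section;
- resistant share f = 5-20% of each arm;
- death before transfer e = 10-30% of resistant patients on colistin, 10% on ETX2514SUL;
- later death l = 20-50% of those who transfer.

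With N = 100(1 - f) and R = 100f, mortality in an arm is:
- as written: (N p + R e)/(N + R e);
- all randomized: [N p + R e + R(1 - e) l]/100.

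Differences are ETX2514SUL minus colistin. The gap is the as-written difference minus the all-randomized one; a negative gap means that the as-written figure looks better for ETX2514SUL.

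*Worked case:* f = 20%, e = 20% v 10%, l = 30% in both arms.
- As written: colistin 36.8/84 = 43.8%; ETX2514SUL 30.8/82 = 37.6%; difference -6.2 points.
- All randomized: colistin (32.8 + 4 + 4.8)/100 = 41.6%; ETX2514SUL (28.8 + 2 + 5.4)/100 = 36.2%; difference -5.4.
- Gap: -0.8.
- If l is instead 50% in ETX2514SUL-origin transfers, that arm becomes (28.8 + 2 + 9)/100 = 39.8%, the all-randomized difference is -1.8, and the gap is -4.4.

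*Over the whole range:*

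| Post-transfer mortality | Gap, points | Where the extremes fall |
|---|---|---|
| Equal in both arms | -1.6 to about 0 | -1.6 at f = 20%, colistin e = 30%, l = 50% (-7.6 v -6.0) |
| Varied 20-50% by arm | -6.3 to +4.5 | f = 20%, e = 10% in both arms; l = 20% colistin v 50% ETX2514SUL gives -4.9 v +1.4; the reverse gives -4.9 v -9.4 |
| Equal, f = 5% only | -0.3 to about 0 | |
| Varied, f = 5% only | -1.6 to +1.1 | |

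Not all of the equal-mortality gap is selection. At f = 20% with early death 10% in both arms, the figures are -4.9 v -4.0, a gap of -0.9 that comes only from diluting the contrast with patients who fare alike.

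**4. Scale.** The 95% CI half-width at 100 per arm is 1.96 x sqrt(0.4723/100) = 13.5 points, or 14.5 with the continuity correction.

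**The case against.** The best defence is that the all-randomized comparison is already planned. The SAP 9.3.1 sensitivity bullet restores the transfers in ITT, SAP 5.4 seeks Day 28 status for everyone randomized, and SAP 9.3.1 repeats its analyses with consent withdrawals included. On this view only a label is in dispute. The label also carries little formal weight: secondary endpoints get counts and confidence intervals, no success criterion rests on ITT, and the exclusion is stated openly.

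Much of this stands. A reader might infer that transfers vanish from every Part A efficacy analysis, or that nothing answers the all-randomized objective. The documents do not support either reading, because of that sensitivity bullet.

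The defence is also right about size. Exclusion 27 (Protocol 4.2) bars known colistin resistance from Part A, transfer applies to either arm on a baseline isolate, and after transfer both groups are assigned the same Part B regimen. The wider range above comes almost entirely from letting post-transfer mortality differ by arm, which nothing in the documents supports.

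What the defence does not remove is the contradiction. The bullet is a sensitivity analysis of the primary endpoint, not the named secondary endpoint, and it does not fix the arm. Two ITT mortality results would be produced, and the one holding the secondary place would be the one that does not meet the ITT definition.

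**Conclusion.** The point holds for the secondary endpoint of 28-day mortality in ITT. As written, SAP 9.1.3, 9.3 and 9.3.2 contradict SAP 8.1, fall short of the SAP 2.2 objective, and extend to ITT an exclusion that the protocol confines to the CRABC m-MITT Population. This is an error in a stated rule rather than a missing detail. The primary analysis is not affected.

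The numerical effect is unknown. Under the assumptions above it is up to about 1.6 points in favour of ETX2514SUL when post-transfer mortality is equal across arms. It can go either way, from -6.3 to +4.5, when that mortality is allowed to differ by arm. A reader might infer a demonstrated bias of several points; the documents do not support that, since they give neither a transfer rate nor outcomes after transfer. Confidence is high in the contradiction and low in any particular size.

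**What to change.** In SAP 9.1.3, 9.3 and 9.3.2, exempt 28-day mortality in ITT from the transfer exclusion. State that the secondary ITT endpoint includes every patient randomized in Part A, in the arm as randomized, with deaths counted from the start of Part A through Day 28 regardless of transfer. Apply the same rule to the repeat that leaves out consent withdrawals. Report the transfer-excluded version as supportive and do not call it ITT. The descriptive Part B summary of transferred patients can stay.

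The cost is SAP wording. The survival data are already sought for all randomized patients and the analysis is already programmed for as a sensitivity analysis. The one small drawback is dilution: transferred colistin patients go on to receive ETX2514SUL, so the all-randomized contrast mixes regimens in that subset. Keeping the transfer-excluded analysis as supportive lets readers see how much this matters.
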